### DATA ANALYSIS

Baseline demographic and clinical characteristics for randomized groups will be compared using chi-square tests for categorical variables, and ANOVA or Kruskal-Wallis tests for continuous variables. Continuous variables will be examined for adherence to normal distribution using normal probability plots and Kolmogorov-Smirnov tests. If normality not satisfied and transformations do not help with achieving normality, alternative analytic strategies will be considered such as generalized estimating equations or nonparametric methods. Dropouts and completers will be compared. Analyses will be intent-to-treat; patients will be followed regardless of treatment completion to minimize missing data. Primary outcomes will be tested at two-sided 0.05 significance level. Secondary analyses will be adjusted for multiple tests using Bonferroni correction.

Overall Data Analysis Strategy will involve MIXED EFFECTS MODELS (Diggle et al, 2002, Gueorguieva & Krystal, 2004) to compare treatments. These models allow for different numbers of observations per subject, use all available data on each subject, and are unaffected by randomly missing data. Further advantage is capacity to test and account for individual-difference contributions to treatment outcomes (Cudeck, 1996; Cudeck & Klebe, 2002; Hedeker et al., 1996; Hedeker & Gibbons, 1996; Singer, 1998). They provide flexibility in modeling the correlation structure of data. In models for each outcome, we will include fixed effects of time, treatment, and interaction between time and treatment, and random subject-level effects. Because we cannot a priori predict the shape of responses over time in each arm of the trial we will first treat time as a categorical predictor and will then test for polynomial trends over time. We will consider different error structures (e.g., AR1, independence) and select the best fitting one based on information criteria. We will

compare dropout patterns between groups and if there are concerns of informative dropout or informative intermittent missing data, we will use pattern mixture models (Hedeker & Gibbons, 1997) to perform sensitivity analyses.

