(1) **STAGE 1 – Primary Outcomes Aim 1 and Secondary Outcomes Aim 2a:** Compare LDX and CBT effects, alone and in combination, for acute BED outcomes. Analyses examining the co-primary outcomes (reduction in binge-eating and percent weight loss) and examining the secondary outcomes (binge remission, eating disorder psychopathology, depression, metabolic variables) will be intent-to-treat using mixed-effects models per the overall strategy described above. Mixed-model analyses on continuous (or pseudo-continuous) data will use SAS PROC MIXED; mixed-model analyses on binary variables will use SAS PROC GLIMMIX. Logistic regression will be used for categorical outcomes (i.e., remission from binge-eating (defined as 0 binges/past 28 days on EDE interview). Significantly greater reductions in binge eating in CBT and CBT+LDX groups compared to LDX, and weight loss in LDX and CBT+LDX compared to CBT will be considered supportive of our primary aim hypotheses. We do not anticipate significant differences between CBT and CBT+LDX on binge eating and between LDX and CBT+LDX on weight loss but the mixed model approach will allow us to estimate the magnitude of the effects with associated confidence intervals.

(2) **STAGE 1 – Secondary Outcomes Aim 2b:** Explore conceptually and empirically supported predictors, moderators, and mediators for the primary outcomes (reductions in binge-eating and weight loss) and secondary categorical outcome (binge-eating remission). We will use the Kraemer et al (2002) approach to assess predictor, moderator and mediator effects by adding potential predictor, moderator and mediator variables to the models above. Predictors will be identified as variables with significant main effects on the outcome, moderators as variables with significant interactions with treatment on the outcome, and mediators will need to be significantly affected by treatment, to be related to the outcome and have main or interactive effects with treatment on the outcome. We will explore two empirically-supported predictors and moderators of BED outcomes – overvaluation of shape/weight (EDE) and depression (BDI-II) ([name], Masheb et al., 2012; [name] et al., 2013). It is necessary to test previous findings to establish them specifically for CBT and LDX treatments to inform prescription (i.e., for whom these “leading” treatments work best).

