**(5) Secondary Aim:** Generate estimates of cost-effectiveness. We will compute within-study costs for CBT, LDX, CBT+LDX and SMART Stage 2 interventions. Repeated assessments will track additional clinician visits and medication use in our RCT as well as outside treatment contacts through the 18-months. SF-12, administered pre- and post-treatments and at follow-ups, will be used to calculate quality-adjusted life years (QALY) following established methods (Revicki et al., 2005) also used in BED studies of cost-effectiveness specifically of LDX (Agh et al., 2016) and CBTgsh (Lynch et al., 2010; Dickerson et al., 2011), as well as for obesity (Tsai et al., 2005; Malone et al., 2005) including obesity medications (Ara et al., 2012), and for similar SMART designs (switching medication for initial non-responders) in depression (Singh et al 2017). We will calculate incremental cost-effectiveness ratios (ICERs) for the various arms; in these ICERs, the numerator will be the incremental medical cost and the denominator will be the incremental effectiveness of the specific treatment compared to CBT. Confidence intervals for the ICERs will be determined using non-parametric bootstrapping. These ICERs will be compared to the two previous BED (Agh et al., 2016; Lynch et al., 2010) analyses and inform subsequent more definitive larger-scale effectiveness studies.

**POWER ANALYSIS:** We calculated our sample size to have at least 80% power at 2-tailed alpha level 0.025 (adjust for 2 outcomes) to detect clinically meaningful effects in Stage 1 for co-primary outcomes (binge eating and weight loss) and Stage 2 for primary outcome (relapse by initial Responders) at 2-tailed level of 0.05 according based on documented effects of the two treatment components (LDX and CBT). In Stage 1, with 180 subjects total (60 per treatment group), accounting for up to 20% dropout, we can detect medium effect sizes ( $d=0.64$ ,  $f=0.32$ ) for the between group comparisons with more than 80% power at two-sided alpha level of 0.025. These effect sizes are smaller than the effect sizes calculated based on data (Telch et al., 1990; [name] et al., 2005; McElroy et al., 2015, McElroy 2016) which ranged  $d=0.69$  to  $d=0.78$  for the comparison of CBT to LDX on binge-eating and was  $d=1.53$  for LDX vs CBT on percent weight loss. Dropout

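### The analysis section tests primary outcomes at two-sided 0.05, but the two Stage 1 co-primaries were sized at 0.025 each and the plan does not say which level applies

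*Combined protocol and SAP*

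**What the plan says.** Section 13 of the combined protocol and SAP gives two significance levels for the Stage 1 co-primary outcomes.

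- **DATA ANALYSIS, opening paragraph:** "Primary outcomes will be tested at two-sided 0.05 significance level". The sentence is not limited to one stage or outcome. The next one reads "Secondary analyses will be adjusted for multiple tests using Bonferroni correction", so the only multiplicity correction in the analysis text is for secondary analyses.
- **DATA ANALYSIS, item (1):** Stage 1 has "co-primary outcomes (reduction in binge-eating and percent weight loss"). Two pairwise contrasts are named for each: CBT and CBT+LDX against LDX on binge-eating, and LDX and CBT+LDX against CBT on weight.
- **POWER ANALYSIS:** Stage 1 is sized for "at least 80% power at 2-tailed alpha level 0.025 (adjust for 2 outcomes"). The level is repeated for the d=0.64 calculation, "for the between group comparisons with more than 80% power at two-sided alpha level of 0.025", and used again for Stage 1 remission. The 0.05 level is given to "Stage 2 for primary outcome (relapse by initial Responders) at 2-tailed level of 0.05".

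Nothing states that the 0.05 in the analysis text is a family-level alpha to be split, and nothing states whether Stage 1 succeeds on either co-primary or only on both.

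**The concern.** An analyst works from the analysis text. Read literally, it tests each Stage 1 co-primary at 0.05 and drops the two-outcome correction that the sample size already pays for. A co-primary result with p between 0.025 and 0.05 would be significant under the analysis text and not significant under the power text. The level for a primary outcome would then be open to choice once the data are known. If either co-primary can carry a claim, two tests at 0.05 can also take Stage 1 error above 5%.

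**Working it through.** **Inputs.** From POWER ANALYSIS: 180 randomised, 60 per arm, up to 20% dropout, so 60 × 0.8 = 48 evaluable per arm; detectable d=0.64; expected d of 0.69 to 0.78 for CBT against LDX on binge-eating and 1.53 for LDX against CBT on percent weight loss. The correlation between the outcomes is not given; 0 to 0.9 is assumed.

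**1. The plan's own figure.** Two-sample t test, noncentrality d × √(n/2) = 0.64 × √24 = 3.135, df = 94.

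- At 0.025 (critical t 2.278): power 80.3%, which reproduces the stated figure of more than 80%.
- At 0.05 (critical t 1.986): power 87.4%.
- Smallest evaluable n per arm for 80% power: at 0.025, 48 (47 gives 79.4%), and 48/0.8 = 60 randomised, exactly as planned. At 0.05, 40 (39 gives 79.7%), and 40/0.8 = 50 randomised.

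The planned size therefore follows from 0.025.

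**2. Error with one test per outcome.** Conditions: both nulls true, either outcome counts, either direction counts. At correlation 0 the error is 1 − (1 − α)². For α=0.05 this is 1 − 0.95² = 9.75%; for α=0.025 it is 1 − 0.975² = 4.94%. For positive correlation it is 1 − P(|Z₁|<c, |Z₂|<c) from the bivariate normal.

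| Correlation | 0.05 each | 0.025 each |
|---|---|---|
| 0 | 9.75% | 4.9% |
| 0.5 | 9.1% | 4.6% |
| 0.9 | 7.0% | 3.6% |

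Simulation with t statistics agrees, reaching 9.8% at correlation 0 for 0.05 each.

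**3. Error across the four named contrasts.** Simulated with both outcomes null, three arms of 48, 141 df, correlation 0 to 0.9; any one significant contrast counts.

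| What counts as an error | 0.05 per test | 0.025 per test |
|---|---|---|
| Hypothesised direction only | 8.7–8.9% | 4.5–4.6% |
| Either direction | about 14–17% | 7.4–9.1% |

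**4. If the weight effect is real.** At d=1.53 the weight null is false. With one test per outcome, the only Stage 1 error left is on binge-eating: 5% under the analysis text, 2.5% under the power text.

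**5. How often the two levels disagree.** The chance that p falls between 0.025 and 0.05 is the power at 0.05 minus the power at 0.025, with 48 per arm.

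| Comparison | d | Power at 0.05 | Power at 0.025 | Difference |
|---|---|---|---|---|
| Binge-eating, CBT vs LDX | 0.64 | 87.4% | 80.3% | 7.1% |
| Binge-eating, CBT vs LDX | 0.69 | 91.7% | 86.3% | 5.4% |
| Binge-eating, CBT vs LDX | 0.78 | 96.6% | 93.7% | 2.9% |
| Weight, LDX vs CBT | 1.53 | above 99.9% | above 99.9% | essentially 0 |

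**The case against.** **The 0.05 may be a family-level alpha.** The sentence does not say each or all. Both statements sit in section 13, and 0.05/2 = 0.025 fits an overall level that the power paragraph then splits. The documents do not exclude this reading, but they do not state it either. If it is what the sponsor meant, the same one-sentence correction records it.

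**Both outcomes may be required.** Item (1) joins the binge-eating and weight hypotheses with *and*. If both had to succeed, 0.05 each would give only about 0.25% (correlation 0) to 3% (correlation 0.9) with both nulls true, and no correction would be needed. But the power paragraph does correct for two outcomes, which would serve no purpose under that rule. The Statement of Purpose also lists the outcomes separately as (1a) and (1b). An either-outcome reading is the better supported one, though it is inferred.

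**The inflation depends on how errors are counted.** This stands. With one contrast per outcome and only the hypothesised direction counted, 0.05 each cannot exceed 2 × 0.025 = 5%. The 7.0–9.8% needs both nulls true, and the plan expects a large weight effect. A reader might infer that the trial will run at 7–10% error; the documents do not support that without the conditions in step 2.

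**The correction does not settle everything.** This also stands. Counting either direction, the four contrasts still carry 7.4–9.1% at 0.025 per test. A reader might infer that restoring 0.025 fully controls Stage 1 error; on that standard it does not.

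**The practical effect is modest.** The window in which the conclusion changes is about 3–7% for one comparison and nil for the other. The protocol says the study does not meet NIH Phase III criteria and is not meant to support a new indication. That limits the consequence, but does not remove the contradiction.

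**Conclusion.** The concern holds as an unreconciled contradiction about the significance level of the Stage 1 co-primaries. The sample size shows that 0.025 is the design level; the analysis text, read literally, gives 0.05.

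The size depends on the error standard, and one standard has to be kept throughout:

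- One test per outcome, either direction: 7.0–9.8% against 3.6–4.9%.
- Four contrasts, hypothesised direction: 8.7–8.9% against 4.5–4.6%.
- Four contrasts, either direction: about 14–17% against 7.4–9.1%.

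All three rest on both nulls being true, either outcome counting, and an assumed correlation of 0 to 0.9. If the weight effect is real, the one-test-per-outcome error is 5% against 2.5%. The power reproduction needs none of these assumptions. Nothing here shows the sample size to be wrong, and Stage 2 relapse at 0.05 is consistent in both places.

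**What to change.** Replace the sentence on primary outcomes in the opening paragraph of DATA ANALYSIS with:

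*Each Stage 1 co-primary outcome (binge-eating, percent weight loss) will be tested at two-sided 0.025; Stage 2 relapse will be tested at two-sided 0.05.*

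This adopts the levels already in the POWER ANALYSIS paragraph. It costs one sentence and changes neither the 180 randomised nor the stated power (80.3% at d=0.64 with 48 evaluable per arm). It should be made before the Stage 1 comparisons are run.

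A rule for reading the four Stage 1 contrasts is a separate, optional choice. If only the hypothesised directions count, 0.025 per test already holds error to about 4.5–4.6%. If results in either direction are to count as separate claims, a Holm procedure or an omnibus gate within each outcome would be needed to bring the 7.4–9.1% down. That has a price: power for CBT against LDX at d=0.64 falls to about 70–78%, depending on the rule and on where the combination arm lies, so the claim of more than 80% would have to be restated.

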**STAGE 1 RCT – Secondary Aims:**

(2a) *Examine the effectiveness of CBT, LDX, and CBT+LDX for BED on secondary outcomes: categorical remission (zero binges/ 28 days), eating-disorder pathology, and depression.*  
 (2b) *Explore predictors, moderators, and mediators of primary treatment outcomes (reductions in binge-eating and weight) and in secondary categorical outcome (binge-eating remission).*

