#### **Assessment of Treatment Outcome and Time Course.**

Primary Measures: (1) Binge-eating frequency (EDE); (2) weight (measured weight and height and BMI); for Stage 2 LDX vs Placebo test: "Relapse" to DSM-5 threshold of once-weekly binge eating on EDE

Secondary Measures: (1) "remission" (zero binges past 28 days on EDE; eating disorder pathology (EDE global), depression (BDI-II); for exploration of mediators: (2) eating behaviors (EDE, TFEQ, FCI-II), executive control and impulsivity (BIS-11, DDT, Trails) and selected metabolic measures (lipid profiles, HbA1c, blood pressure, HR) to characterize metabolic outcomes and allow comparison with RCTs for LDX and NB.

**Figure 2.** Grid depicting when each measurement is obtained

Assessment Points	BASELINE (2 MTG)	DURING RX STAGE 1 1-MONTH	DURING RX STAGE 1 2-MONTH	POST RX STAGE 1 3-MONTH	DURING RX STAGE 2 4-MONTH	DURING RX STAGE 2 5-MONTH	POST RX STAGE 2 6-MONTH	6 AND 12- MO FOLLOW- UP (18 MONTH TOTAL)
MINI Psychiatric Interview, Height, Credibility,	•							
EDE Interview, SF-12, GPAQ, Lipid Profile, HbA1C, Glucose	•			•			•	•
EDE-Q-I, BDI-II, GLTEQ, Weight, BP, HR	•	•	•	•	•	•	•	•
TFEQ-Restraint	•	•		•			•	•
DDT	•	•		•			•	
FCI-II, PFS	•	•		•	•		•	
BIS-11	•	•		•	•		•	•
ELOCS	•	•		•				
Trails, YFAS, BRS, Amphetamine Testing	•			•			•	
Placebo Ratings					•		•	
Start of New Treatments				•			•	•
Medical History Creatinine w/ EGFR PSQI	•			•				
Adverse Events		•	•	•	•	•	•	
Insulin	•			•				

Liver Function	•			•	• (Non- responde rs only)			
Pregnancy Test	•			•				

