rate estimated based on completion rates for [name] RCTs with BED: 87% in [name] & Masheb, 2005; 84% in [name], White et al., 2014; and previous grant 2R01 DK49587-15 testing stepped care multi-modal treatment and obesity medication along with the LDX RCTs (McElroy et al., 2015, 2016). For binary outcomes (remission), we can detect the following clinically meaningful differences in proportions (63% vs 35%, 66% vs 38%) at 2-tailed alpha of 0.025 in Stage 1. These are in line with observed proportions for CBT (62% by Wilson et al (2010); 64% by Striegel-Moore et al. (2010); LDX (40% and 36% by McElroy et al (2015; 2016) in BED subjects uncomplicated by co-morbidity. Thus, we are well powered for realistic and meaningful effect sizes for both primary and secondary outcome variables. In Stage 2, we expect to randomize 65-70% of subjects as Responders (per McElroy et al 2017); thus we anticipate to have about 80 subjects from the LDX and CBT+LDX groups for the comparisons of interest. Assuming further 20% dropout, we will have 64 subjects with complete data at the end of Stage 2. With this sample size, we have 89% power at two-sided alpha level of 0.05 to detect differences in relapse reported by Hudson et al (2015) of 4% vs 32% (LDX vs placebo). We would have over 80% power to detect differences for the following rates between placebo and LDX: 10% vs 39%, 15% vs 46%, 25% vs 58%.

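### Remission power is stated at two-sided 0.025, but the Bonferroni rule for secondary analyses puts remission at 0.0167 or lower, and the family that sets the level is not defined

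*Combined protocol and SAP*

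**What the plan says.** The opening paragraph of Data Analysis (section 13, Statistical Considerations) sets two rules: "Primary outcomes will be tested at two-sided 0.05 significance level" and "Secondary analyses will be adjusted for multiple tests using Bonferroni correction". It names no family, no number of tests and no exemption.

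The list of Stage 1 secondary outcomes depends on where one looks:

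- Stage 1 Secondary Aims: "categorical remission (zero binges/ 28 days), eating-disorder pathology, and depression", which is three outcomes.
- Data Analysis, item (1): "secondary outcomes (binge remission, eating disorder psychopathology, depression, metabolic variables", which is four, with the metabolic variables as one entry.
- Assessment of Treatment Outcome and Time Course, Secondary Measures: "selected metabolic measures (lipid profiles, HbA1c, blood pressure, HR) to characterize metabolic outcomes". Here the metabolic entry covers four kinds of measurement, including blood pressure and heart rate.

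The Power Analysis sizes Stage 1 for "at least 80% power at 2-tailed alpha level 0.025 (adjust for 2 outcomes", so 0.025 comes from the two co-primaries. It then says of remission: "we can detect the following clinically meaningful differences in proportions (63% vs 35%, 66% vs 38%) at 2-tailed alpha of 0.025 in Stage 1". The paragraph goes on to claim good power for primary and secondary outcomes alike.

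**The concern.** Remission is secondary in all three lists, so the Bonferroni rule governs it. Its power is nevertheless quoted at a level borrowed from the co-primary outcomes. A Bonferroni level of 0.025 from an overall 0.05 needs a family of exactly two, and none of the Stage 1 lists has two entries. The quoted detectable differences therefore belong to a test that the plan will not run.

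Two things are at stake. First, remission is the main categorical efficacy result, and readers are told that the trial is adequately powered for it. Second, heart rate and blood pressure enter the corrected Stage 1 set through the metabolic entry. Increased heart rate is a listed side effect of LDX, and two of the three Stage 1 arms receive LDX. A multiplicity penalty guards against false efficacy claims. Applied to a safety measure, it makes a real between-arm rise harder to declare. Section 13 specifies no separate between-arm safety analysis.

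**Working it through.** **Inputs from the Power Analysis.** There are 60 per arm and up to 20% dropout, so 60 × 0.8 = 48 per arm. The remission pairs are 63% vs 35% and 66% vs 38%, at two-sided 0.025. The remission sentence does not repeat a power figure. I take the 80% stated for the design, and the reproduction below supports that.

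**Formula (two proportions, pooled variance).** Power = Φ{ [ |p1 − p2|·√n − z·√(2·p̄·(1 − p̄)) ] / √(p1(1 − p1) + p2(1 − p2)) }, where z is the two-sided critical value.

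For 63% vs 35%:

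- p̄ = 0.49, so √(2 × 0.49 × 0.51) = 0.7070.
- √(0.2331 + 0.2275) = 0.6787.

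**Reproducing the plan's figure at 0.025 (z = 2.2414).**

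- n = 60: (2.1689 − 1.5846)/0.6787 = 0.861, power 80.5%. The other pair gives 80.6%.
- n = 48: (1.9399 − 1.5846)/0.6787 = 0.524, power 70.0%. The other pair also gives 70.0%.

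Other methods at n = 48 give 66.3% (Fisher), 70.5% (arcsine), 73.1% (unpooled) and 73.6% (exact chi-square), and none reaches 80%. The remission figure therefore uses all 60 per arm with no loss. By contrast, the plan's d = 0.64 for continuous outcomes reproduces at 48 per arm (80.3% by t-test), so the two statements in that paragraph rest on different sample sizes.

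**Applying the Bonferroni rule.** The level is 0.05/k. The plan does not give k, so each row is an assumption about the family.

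| Family | k | Level | Power, 60 per arm | Power, 48 per arm |
|---|---|---|---|---|
| Level used in the Power Analysis | 2 | 0.0250 | 80.5% | 70.0% |
| Stage 1 Secondary Aims list | 3 | 0.0167 | 75.9% | 64.2% |
| Data Analysis item (1), metabolic counted once | 4 | 0.0125 | 72.4% | 60.1% |
| Three outcomes plus lipids, HbA1c, blood pressure, heart rate | 7 | 0.0071 | 65.3% | 52.2% |
| Three outcomes × three pairwise contrasts | 9 | 0.0056 | 62.1% | 48.8% |
| Seven outcomes × three contrasts | 21 | 0.0024 | 51.2% | 38.0% |

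Check for k = 3 (z = 2.3940): (2.1689 − 1.6925)/0.6787 = 0.702, power 75.9%. For 80% power, 66 evaluable per arm are needed at k = 3 and 70 at k = 4.

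**How much is due to blood pressure and heart rate.** Removing both takes k from 7 to 5, and power at 60 per arm from 65.3% to 69.6%. With contrasts counted, k goes from 21 to 15, and power from 51.2% to 55.5%. That recovers about 4 points. Most of the gap comes from the undefined family and the borrowed 0.025.

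**Effect on a heart-rate contrast.** The plan gives no expected shift, so the size is assumed. Power is Φ(d·√(n/2) − z) at 60 per arm:

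- d = 0.5: 78.2% at 0.05, and 51.9% at 0.05/7.
- d = 0.3: 37.6% at 0.05, and 14.8% at 0.05/7.

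**The case against.** **The family is not fixed.** With three outcomes the level is 0.0167, only modestly below 0.025. A reader might infer that remission is tested far below its planned level, but that holds only if every metabolic variable or contrast is counted, which the plan does not say. This limits the size of the finding but does not remove it, since every documented list gives a level below 0.025.

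**Sixty per arm may be intended.** Analyses are by intention to treat and participants are followed after stopping treatment, so the full 60 could be the denominator. The plan does not say how remission is scored for someone with no assessment, and the same paragraph allows for 20% dropout. Even with 60 per arm, the Bonferroni rule gives 75.9% or 72.4%.

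**Harm is not hidden.** A reader might infer that the correction suppresses evidence of known harms of both drugs. The documents do not support that:

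- Bonferroni raises a significance threshold; it does not remove estimates.
- Adverse-event collection, the individual blood-pressure and heart-rate triggers for physician review (Minimizing Risks, Assessments) and the twice-yearly DSMB reports use no corrected p-value.
- Heart rate is a listed effect of both drugs, but raised blood pressure is listed only for NB. NB is not given in Stage 1, and the secondary list for its Stage 2 comparison omits both measures.
- In a weight-loss trial, blood pressure may also be read as a possible benefit.

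What stands is narrower: Stage 1 heart rate and blood pressure fall under an efficacy-type correction, with no separate safety analysis in section 13.

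**Bonferroni is valid.** It is, and choosing Holm is a gain in efficiency rather than the repair of an error.

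**Conclusion.** The concern holds for remission. The plan's own rule puts remission at 0.0167 or 0.0125 on its two explicit Stage 1 lists, not at 0.025. Power for 63% vs 35% is then 75.9% or 72.4% at 60 per arm, and 64.2% or 60.1% at 48 per arm. At 48 per arm it is only 70.0% even at 0.025. The general claim of good power for secondary outcomes is therefore not met for this one.

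These figures assume an overall 0.05 for the secondary family, a pooled two-proportion test and a family size that the plan leaves open. A larger family makes them worse.

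The vital-signs part is secondary. A between-arm difference in Stage 1 would be harder to declare, but nothing in the documents shows that safety oversight depends on that test.

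**What to change.** In Data Analysis:

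- Define the adjusted family separately for each stage, as its named secondary efficacy outcomes. For Stage 1 these are remission, EDE global and BDI-II. For Stage 2 they are the secondary outcomes named for the responder comparison and those named for the non-responder comparison. A family limited to the Stage 1 three would leave the Stage 2 secondary efficacy outcomes uncovered.
- State whether pairwise contrasts count. For the Stage 1 family this decides between k = 3 and k = 9.
- Replace Bonferroni with Holm, which controls the same error rate and rejects everything that Bonferroni rejects.
- Report blood pressure, heart rate and laboratory measures as safety or descriptive estimates with unadjusted 95% confidence intervals.

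In the Power Analysis, restate remission power at the resulting level and with the 20% dropout. Under Holm with k = 3 and 48 per arm it lies between 64.2% (level 0.05/3) and 79.3% (level 0.05), depending on the other outcomes.

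The cost is wording, a less favourable stated power, and the loss of simple simultaneous confidence intervals, which Holm does not give. Sample size and data collection do not change.
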